## I. INTRODUCTION

Lumbar degenerative disc disease is a common disorder that may cause debilitating symptoms. Although there is discrepancy in the prevalence estimates of the morphological changes associated with degeneration (Battie et al. 2004), lumbar degenerative disc disease is a major cause of chronic disability (Modic and Ross 2007). Risk factors include genetic predisposition, trauma, impaired nutrition of the intervertebral disk, mechanical loading and aging (Battie et al. 2004; Modic and Ross 2007). Patients with lumbar disc disease most commonly present with low back pain and radiculopathy, but many are asymptomatic (Modic and Ross 2007).

When conservative measures such as medication and physical therapy fail, lumbar spinal surgery is used to treat degenerative disc disease. Spinal fusion surgery limits movement of the vertebrae adjacent to the affected intervertebral disc. It typically consists of spinal instrumentation to secure the vertebrae, and bone graft material, to allow the vertebrae to fuse together (Rutherford et al. 2007).

One of the major controversies surrounding lumbar spine fusion is the choice of ideal graft material used to facilitate fusion. Commonly studied properties of graft materials include osteoconduction (scaffolding for bone re-growth), osteoinduction (growth factors that induce bone growth), and osteogenesis (living cells that produce new bone); (Vaccaro 2002). An ideal allograft material is one that is safe, effective in forming bone, forms bone where intended without excessive bone growth, can integrate with the host, and is cost effective.

Autogenous bone graft, obtained from the iliac crest, has traditionally been considered the gold standard. The advantages of an autogenous graft include high fusion rates, good incorporation, predictable results, osteoconduction, osteoinduction, osteogenesis, lack of immunogenicity, circumvents risk of disease transmission from another donor, and is cost-effective. (Arrington et al. 1996; Chau and Mobbs 2009). However, iliac crest harvest is associated with morbidity at the harvesting site. Complications include pain, numbness, injury to nerves or arteries, infection, seromas, hematomas, peritoneal perforation, herniation of abdominal contents, bone fracture, and cosmetic concerns about the scar (Kurz et al. 1989; Arrington et al. 1996; Schwartz et al. 2009). Post-operative pain may lead to a longer hospital stay, and/or possibly lead to difficulty performing basic daily activities (Dusseldorp and Mobbs 2009; Schwartz et al.

2009). Other drawbacks include limited quantity and quality of bone graft, increased blood loss and increased operating time (Chau and Mobbs 2009).

There are several commercially available bone graft substitutes with differing properties. Allograft is bone obtained from cadaveric sources, which has been treated to decrease its immunogenicity and risk of disease transmission. It is osteoconductive, minimally osteoinductive, slower to incorporate and produces more variable results than autogenous bone graft (Vaccaro 2002; Miyazaki and Tsumura 2009). Ceramics have been used in spinal fusions, as they are osteoconductive, available in large quantities and are sterile. However, they are brittle and can withstand little force (Vaccaro 2002; Miyazaki and Tsumura 2009). Demineralized bone matrix (DBM) is both osteoconductive and osteoinductive. It is produced from cortical allograft bone that has undergone acid extraction, removing its mineral component, but retains many proteins, including growth factors (Miyazaki and Tsumura 2009). Osteoinductive growth factors have also been used as bone graft substitutes, and the most studied and used factor is recombinant human bone morphogenetic protein-2 (rhBMP-2). Since its introduction commercially in 2002, rhBMP-2 has shown rapid and robust bone fusion, and gained widespread use, despite its high cost. However, reports of serious complications have emerged, including ectopic bone formation, infection, urogenital events, carcinogenicity and others (Carragee et al. 2011). This lead to the Yale University Open Data access (YODA) Project to re-analyze all the clinical data gathered by the manufacturer of rhBMP-2 (Infuse; Medtronic). The results were published in June 2013, in a special edition of the Annals of Internal Medicine. Two independent groups (Fu et al. 2013; Simmonds et al. 2013) found that rhBMP-2 was not better than autogenous bone graft in terms of fusion, pain or function, but posed an increased risk of adverse events. Other emerging options for bone graft substitutes include autologous platelet concentrate, mesenchymal stem cells and gene therapy (Miyazaki and Tsumura 2009).

Therapeutic use of amniotic fluid and the amniotic membrane has existed in medicine for decades in many different capacities (Shimberg 1938). Some applications include healing of the eye, soft-tissue wounds, and bone fractures (Karaçal et al. 2005; Kerimoğlu 2008). Recently, amniotic epithelial cells have been shown to express stem cell markers of pluripotency, including octamer-binding protein 4 (*Oct-4*) and *Nanog* (Miki and Strom 2006; Miki 2011). Cells isolated from the amnion are able to differentiate into all three germ layers: endoderm, mesoderm and ectoderm (Toda et al. 2007).

Amniotic fluid and membrane contain mesenchymal stem cells (MSCs), which may be useful in graft material for bone fusion for several reasons. They have been shown to have osteoinductive and osteogenic properties, and therefore can regenerate bone. They have been shown to selectively adhere to bone substrate and are unlikely to be rejected since they are immune privileged (they do not express human leukocyte antigen (HLA) class II molecules). Also, stem cells from amniotic origin have low risk of tumorigenicity (Siegel et al. 2007). Finally,

stem cells from an amniotic source do not pose ethical issues, as there is no risk to the mother or fetus.

NuCel® is a commercially available (NuTech Medical, Birmingham, AL) source of MSCs derived from human amniotic fluid in combination with morselized amniotic membrane tissue. In addition to stem cells, this tissue contains collagen, proteoglycans, hyaluronic acid, trophic proteins including bone morphogenetic proteins (BMPs), and growth factors.

Therefore, the goal of the proposed research is to use NuCel® in the bone graft material applied to patients undergoing posterolateral lumbar spine fusion, to assess its ability to promote bone fusion. Its safety and efficacy will be compared to a standard allograft material routinely used for this surgery.

## II. METHODS

### *A. Study Population*

Participants will consist of patients presenting with symptomatic, one or two-level lumbar degenerative disc disease, spondylosis or spondylolisthesis. They must have failed traditional conservative treatment measures, such as pain medication, physical therapy, lumbar epidural steroid injections or lumbar bracing support, prior to surgery. They must be candidates for a one or two-level posterolateral lumbar fusion, with instrumentation, with or without laminectomy. The participants are patients that the surgeon would consider as low risk for non-union, and would have received only demineralized bone matrix (DBM) bone graft material without any other graft material, in particular, no recombinant human bone morphogenetic protein (rhBMP-2). Patients who would be considered higher risk of non-union, and who would have typically received rhBMP-2 will be excluded according to the list below.

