### ***B. Hypothesis***

We hypothesize that the NuCel® group will report, on average, Oswestry Disability Index (ODI) scores 10% lower than those of the DBM group. Assuming a baseline ODI score of 52 (SD=8) for the DBM group, 90% power and an a Type 1 error rate of 5%, a sample size of 42 patients (21 per group) would be sufficient to detect a 10% difference between groups using a repeated measures design with 6 measurement points. To account for drop-out, loss to follow-up, and/or refusal to complete study documents at follow-up, we plan to recruit a total of 60 patients (30 per treatment arm).

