### ***C. Study Variables***

#### Clinical outcomes

The following data will be collected at the time of enrollment (pre-operatively), and at 1, 2, 3, 6 and 12 months after surgery: 0-10 numeric pain rating scale for low back and leg pain, Oswestry Disability Index (ODI), and a neurological exam (sensory and motor evaluation). We will also record any adverse events (infection, inflammation, radiculopathy, etc.) that occur intra-operatively through 12 months. Demographic information including gender, age, diagnosis, spinal level for surgery, will be recorded directly into an Excel spreadsheet for each patient.

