### *Sources of Bias*

Efforts were made in designing this study to minimize the chance of study biases. We attempted to minimize the effect of additional medical conditions by having strict exclusion criteria. For example, patients who have any condition, such as diabetes, osteoporosis, or are smokers, are excluded from the study as these factors may have an effect on bone healing. All efforts are made to recruit groups that are as homogenous as reasonably possible. Participant bias will be

mitigated by blinding participants to the intervention they will receive. For clinical outcome measures, evaluator bias is minimized as the data will be collected through objective questionnaires to be filled out by the participants (pain scales, ODI). There is no need for evaluator judgment, which may be subjective, in recording these data. For radiological outcome measures, an independent, blinded radiologist will score the scans, eliminating evaluator bias. The only test that may be subject to evaluator bias is the neurological exam for sensory and motor deficits. Having said that, the neurological exam will be performed by [name], [name], a physician assistant (PA) or a nurse practitioner (NP) who is highly skilled and experienced in evaluating this test.

Since the only experimental intervention is at the time of surgery this study does not depend on patient adherence for the study intervention. The study will, however, depend on patients adhering to follow-up office visits and scans. We expect the “drop-out” rate will be low as most of these visits are required as follow-up to any surgery. Also, the final time point for data collection is 12 months after surgery, therefore, it is unlikely that the patient will seek surgical treatment elsewhere during this time frame.

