#### ***E. Statistical Analysis***

We will first compare the demographic and pre-operative clinical characteristics of the NuCel® and DBM groups to evaluate randomization fidelity. If any characteristics are found to be statistically significant between the groups, this will be accounted for in the analyses of the primary and secondary outcomes. We will describe all categorical variables as percentages and continuous variables with means and standard deviations.

To evaluate our primary outcome we will use a linear mixed model with ODI score as the dependent variable and treatment group and time as independent variables. Mixed models are often preferred over a two-way ANOVA because they allow for incomplete data from participants and do not require a strictly normal distribution in the dependent variable. This model will also be used to evaluate the effect of treatment group on pain scores over time. Statistical significance will be set at  $p < .05$ .

We will report the frequency of observed fusion at the 6-month and 12-month follow-up periods via CT scan by treatment group. If our sample size allows, we will compare the NuCel® and DBM groups on fusion rates at each time point using Fisher’s Exact tests. Statistical significance will be set at  $p < .05$ .

We will report the frequency of adverse events experienced by the NuCel® and DBM groups including negative changes in neurological exam (sensory and motor) findings during the follow-up period.

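### Number of levels can enter the ODI and pain models only through a baseline significance test that would rarely fire, and laminectomy is not named as recorded; pre-specifying both is a cheap gain in precision

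*Combined protocol and SAP*

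**What the plan says.** A. Study Population admits "candidates for a one or two-level posterolateral lumbar fusion, with instrumentation, with or without laminectomy". D. Study Design uses blocked allocation and names no stratification factor.

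The data list under Clinical outcomes reads "Demographic information including gender, age, diagnosis, spinal level for surgery, will be recorded". Number of levels can be derived from spinal level. Laminectomy is not named.

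E. Statistical Analysis gives the ODI model "treatment group and time as independent variables" and uses the same model for pain. It adds a conditional rule: a demographic or pre-operative characteristic that differs significantly between the arms will be accounted for in the primary and secondary analyses. Fusion at 6 and 12 months is reported by arm and, if numbers allow, compared by Fisher's exact test, which takes no covariate.

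**The concern.** Number of levels and laminectomy describe how large the operation is. Both can be fixed as planned surgery before allocation, and either could plausibly affect post-operative disability whatever the graft. If so, leaving them out of the model leaves their variance in the error term.

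The plan's only route to adjustment is a significant baseline difference. In arms of 21 to 30 patients such a test responds only to extreme imbalance, so moderate imbalance would go unadjusted. The route may not exist at all for laminectomy, since nothing commits the trial to recording it. At stake is precision in a small trial, not validity.

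**Working it through.** **Inputs from B. Hypothesis.** The target is "Oswestry Disability Index (ODI) scores 10% lower than those of the DBM group". The mean and SD come from "Assuming a baseline ODI score of 52 (SD=8) for the DBM group", so the difference is 0.10 × 52 = 5.2 points with SD 8 (variance 64). Power is 90% and type 1 error 5% (two-sided assumed), "using a repeated measures design with 6 measurement points". The plan needs 21 per arm and recruits 30.

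**Assumptions, because the documents give no figure.** Two-level share 30-50%; shift D in post-operative ODI for two-level patients of 2-6 points; within-patient correlation ρ.

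**1. The plan's sample size.** For one visit, n per arm = 2 × [8 × (1.960 + 1.282) / 5.2]² = 49.7. For the mean of six visits, multiply by (1 + 5ρ)/6. Setting the result to 21 gives ρ = (6 × 21/49.7 − 1)/5 = 0.31. The stated 21 is therefore attainable, but only at a correlation the plan does not state; at ρ = 0.5 the formula gives 30 per arm. I use both values below.

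**2. How often the conditional rule would act.** The two-level counts in the arms are taken as independent binomials, enumerated exactly, with Fisher's exact test as the baseline check (the plan names no test).

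| Per arm | Two-level share | Gap of 15 points or more | Same gap, test not significant | Test significant |
|---|---|---|---|---|
| 30 | 30% | 20.4% | 17.8% | 2.6% |
| 30 | 40% | 23.5% | 20.9% | 2.6% |
| 30 | 50% | 24.5% | 21.8% | 2.7% |

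Starting from 9 of 30 in one arm, the other needs 18 of 30 before the test is significant; from 15 it needs 24. Either way the gap is 30 points. Close to nine in ten gaps of 15 points or more would not trigger adjustment.

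**3. What adjustment would gain.**
- Variance of a patient's six-visit mean: 64 × (1 + 5ρ)/6 = 27.0 at ρ = 0.307 and 37.3 at ρ = 0.5.
- Surgery cannot affect the pre-operative score, so a shift D at the five later visits moves the six-visit mean by 5D/6.
- At 40% two-level, the variance removed is 0.4 × 0.6 × (5D/6)² = 0.67, 2.67 and 6.00 for D = 2, 4 and 6.
- Power is for a two-sided t-test of 5.2 points, with two degrees of freedom charged for two covariates. Only number of levels is credited with removing variance.

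| Per arm | ρ | Unadjusted | D = 2 | D = 4 | D = 6 |
|---|---|---|---|---|---|
| 21 | 0.31 | 88.5% | 89.2% | 91.4% | 94.7% |
| 21 | 0.5 | 76.8% | 77.4% | 79.6% | 83.5% |
| 30 | 0.31 | 96.8% | 97.1% | 98.0% | 99.1% |
| 30 | 0.5 | 90.0% | 90.5% | 91.9% | 94.2% |

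For example, at 21 per arm, ρ = 0.31 and D = 6, the standard error falls from √(2 × 27.0/21) = 1.60 to √(2 × 21.0/21) = 1.42. The unadjusted 88.5% lies just under 90% because it uses the t distribution, whereas step 1 uses the normal approximation.

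**The case against.** **The plan does have a route to adjustment.** A reader might infer that neither factor can ever enter the models. That is wrong for number of levels, which is recorded and falls under the conditional rule. What stands is that the rule would rarely act. A less conservative baseline test would fire nearer 5% of the time, which does not change the conclusion.

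**This is not bias.** A reader might infer that chance imbalance biases the result. Under randomisation the unadjusted estimate is unbiased and type 1 error is not inflated. A 15-point gap with D = 2-6 moves a post-operative contrast by 0.3 to 0.9 points (0.15 × D), but that variation is already inside the standard error: the 95% half-width at 30 per arm and ρ = 0.31 is 1.96 × √(2 × 27.0/30) = 2.6 points. Imbalance and lost power are one variance component, not two harms. This objection stands in full.

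**The size is assumed.** The documents give no two-level share and no effect of levels or laminectomy on ODI. D = 6 would exceed the whole treatment target. At D = 2 the gain is under one percentage point, and at 30 per arm there is little left to gain when ρ = 0.31. This also stands.

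**Laminectomy may be recorded.** The data list is introduced as a non-exhaustive one, so the omission is silence and not proof. The fair statement is that nothing commits the trial to recording it.

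**The homogeneity statement is no contradiction.** A reader might set "All efforts are made to recruit groups that are as homogenous as reasonably possible" (Sources of Bias) against the mixed operations. In context it follows examples of excluded conditions that affect bone healing, so it concerns comorbidity and not extent of surgery.

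**Fusion is little affected by imbalance.** Suppose 85% of levels fuse and every operated level must fuse. Two-level patients then succeed in 0.85² = 72%, a difference of about 13 points. With 95% of chance gaps within 1.96 × √(2 × 0.24/30) = 0.25, the fusion contrast shifts by up to about 3 points (0.25 × 13). At an assumed 80% overall rate and 30 per arm, its 95% half-width is about 20 points. The documents do not support a claim that the fusion comparison is materially distorted.

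**Conclusion.** The point holds as a low-cost improvement in precision. Operations of different extent are pooled; neither factor is a stratification factor or a pre-specified covariate; number of levels enters only through a test that fires in about 3% of randomisations at 30 per arm; and recording of laminectomy is not assured.

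The gain in power at 21 per arm ranges from under 1 percentage point (D = 2) to about 6-7 points (D = 6), and at 30 per arm from under 1 to about 4 points. These figures assume a 40% two-level share, a shift that persists over all five post-operative visits, and ρ of 0.31 or 0.5. They cover number of levels only; laminectomy was not quantified. The case does not depend on a large effect, because adjustment costs almost nothing even when the effect is small.

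**What to change.** 1. Record planned number of levels (one or two) and planned laminectomy (yes/no) before the envelope is opened. Planned surgery is the right variable because allocation is revealed pre-operatively and the surgeon is not described as blinded, so surgery as performed could be influenced by allocation.
2. In E. Statistical Analysis, pre-specify both as fixed covariates in the ODI and pain models, allowed to act at the post-operative visits, whatever the baseline tests show.
3. Report fusion by arm and number of levels as a descriptive table. State how a patient with one of two levels fused is classed, since the three categories under Radiological outcomes do not say. A stratified fusion test is optional: at 40% two-level the strata hold only about 12 and 18 patients per arm.

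The cost is one added field, a sentence or two in the analysis section and a few degrees of freedom. No visits or patients are added.

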#### Inclusion Criteria

- Between the ages of 18 and 75 years
- Symptomatic, one or two-level degenerative lumbar disc disease, spondylosis or spondylolisthesis
- Failed conservative treatments
- Must be candidates for one or two-level, posterolateral lumbar spine fusion
- Must be able and willing to give Informed Consent
- English-speaking

### Exclusion Criteria

- Smoker (any smoking  $\leq$ 3 months prior to consent); (Patel et al. 2013)
- Patients with poorly controlled diabetes mellitus (HgbA1c  $>$  7%)
- Documented osteoporosis
- Prior lumbar spinal surgery at the same spinal level, or immediately adjacent spine level, to the level being operated on
- Back pain due to infection, tumour, or metabolic bone disease
- Terminal disease, such as HIV infection, neoplasm
- Autoimmune disease, such as rheumatoid arthritis
- Morbid obesity (body mass index (BMI) of 35 kg/m^2)
- Major psychiatric illness in the last year
- History of alcohol or drug abuse in the last year
- Pregnant women

### ***B. Hypothesis***

We hypothesize that the NuCel® group will report, on average, Oswestry Disability Index (ODI) scores 10% lower than those of the DBM group. Assuming a baseline ODI score of 52 (SD=8) for the DBM group, 90% power and an a Type 1 error rate of 5%, a sample size of 42 patients (21 per group) would be sufficient to detect a 10% difference between groups using a repeated measures design with 6 measurement points. To account for drop-out, loss to follow-up, and/or refusal to complete study documents at follow-up, we plan to recruit a total of 60 patients (30 per treatment arm).

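### The 90% power claim counts six ODI scores, one of them pre-operative, and the primary model does not say how that score is used

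*Combined protocol and SAP*

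**What the plan says.** Section II.B (Hypothesis) sets the size of the trial. Its inputs are these: "Assuming a baseline ODI score of 52 (SD=8) for the DBM group, 90% power and an a Type 1 error rate of 5" per cent. On that basis 21 patients per group "would be sufficient to detect a 10% difference between groups using a repeated measures design with 6 measurement points". To cover losses, "we plan to recruit a total of 60 patients (30 per treatment arm"), which allows for 18 of 60, or 30%, being lost.

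Section II.C (Clinical outcomes, and the time-line table under Radiological outcomes) shows what the six points are. The ODI is collected "at the time of enrollment (pre-operatively), and at 1, 2, 3, 6 and 12 months after surgery": one score before surgery and five after.

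Section II.E (Statistical Analysis) gives the primary analysis: "we will use a linear mixed model with ODI score as the dependent variable and treatment group and time as independent variables". Baseline variables enter the primary and secondary analyses only after a test: "If any characteristics are found to be statistically significant between the groups, this will be accounted for in the analyses".

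**The concern.** A repeated-measures sample size cannot be computed without a within-patient correlation, and section II.B gives none. It also gives no correlation structure, sidedness, difference in points, or post-operative mean or SD. The count of six adds a second problem. The graft is placed at surgery, so the pre-operative score cannot carry a treatment effect and the six scores cannot all show the assumed difference.

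Whether this costs power depends on what the model does with the pre-operative score, and section II.E leaves that open. The score could be a sixth outcome, be left out, or become a covariate if the groups happen to differ significantly on it. In the first case the group term averages a zero effect with five real ones. The last makes the primary model depend on the data.

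This is the only power statement for the primary outcome. If the 90% does not belong to the analysis actually run, a null result may be read as stronger evidence against a benefit than the trial can give.

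**Working it through.** **Inputs from the documents.** DBM mean 52, SD 8, 10% difference, 5% type I error, 21 per group, six points (II.B); visits at 0, 1, 2, 3, 6 and 12 months (II.C); group and time as model terms (II.E).

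**Assumptions.** The difference is 10% of 52 = 5.2 points and is constant from month 1. The SD is 8 at every visit, data are complete, there is no true baseline difference, and the test is two-sided. Correlations of 0.3, 0.5 and 0.7 are illustrative.

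**Method.** Under compound symmetry with correlation ρ, a patient's mean over m visits has variance 64 × (1 + (m − 1)ρ)/m. The standard error of the group difference is √(2 × variance/n). Power comes from the noncentral t distribution with 2n − 2 degrees of freedom.

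**1. The plan's own figure.** Let all six visits carry 5.2. At ρ = 0.28 the variance is 64 × 2.4/6 = 25.6, the standard error is √(2 × 25.6/21) = 1.56, and the ratio is 5.2/1.56 = 3.33. Power is 90%. So 21 per group is reproduced if ρ is about 0.28 or less (0.31 by normal approximation). Using only the five post-operative visits, without baseline adjustment, the limit is about 0.25.

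**2. Pre-operative score in the outcome.** With equal weights the group effect is (0 + 5 × 5.2)/6 = 4.33 points.

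| ρ | Variance | SE, 21/group | 4.33/SE | Power, 21/group | Power, 30/group |
|---|---|---|---|---|---|
| 0.3 | 64 × 2.5/6 = 26.7 | 1.59 | 2.72 | 76% | 89% |
| 0.5 | 64 × 3.5/6 = 37.3 | 1.89 | 2.30 | 61% | 77% |
| 0.7 | 64 × 4.5/6 = 48.0 | 2.14 | 2.03 | 51% | 66% |

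Reaching 90% at 21 per group needs ρ of about 0.13 or less.

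**3. Same analysis, autoregressive correlation on the actual schedule.** Take the correlation between visits s and t months as r to the power |s − t|. For one-month correlations r = 0.3, 0.5 and 0.7, power at 21 per group is about 95%, 88% and 76%, and 90% needs r of about 0.45 or less. This structure is favourable because distant visits become nearly independent: at r = 0.7 the 6- and 12-month scores correlate only 0.7^6 = 0.12.

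**4. Pre-operative score as a covariate, five post-operative outcomes.** The effect stays at 5.2. Under compound symmetry the adjusted variance is 64 × [(1 + 4ρ)/5 − ρ²], with 2n − 3 degrees of freedom. It is largest at ρ = 0.4: 64 × (0.52 − 0.16) = 23.04. The standard error is √(2 × 23.04/21) = 1.48, the ratio is 3.51 and power is about 93%. Simulation gives about 92%, because the formula ignores the small loss from chance baseline imbalance. At ρ = 0.3, 0.5 and 0.7 the analytic values are 93.5%, 93.5% and 97.7%. Under the autoregressive structure of step 3 the minimum over r is about 95%.

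**The case against.** The strongest reply is that nothing here is miscalculated. Step 1 shows that 21 per group is attainable, and a low correlation is not impossible. That stands. A reader might infer from the missing inputs that the sample size is wrong or the trial underpowered; the documents support neither.

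The dilution is also conditional. Section II.E does not say that the pre-operative score is an outcome, although the count of six and a model with only group and time make that the most direct reading. The value 4.33 further needs equal weights, complete data and a constant effect; another fitted covariance would weight the visits differently. And if the 10% is meant as an average over all six points, 5.2 is not diluted, but the five post-operative visits must then show 5.2 × 6/5 = 6.24 points. Either way the plan has to say which is meant.

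The recruitment target softens the consequence. Sixty patients are planned, and section II.D (Sources of Bias) expects that the drop-out "rate will be low as most of these visits are required as follow-up to any surgery". With all 30 per group evaluable, the diluted analysis gives 89% at a correlation of 0.3, but still only 77% and 66% at 0.5 and 0.7. The additional patients are there to cover losses, so they do not support the claim made for 21.

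Finally, a reader might take the phrase about pain, "This model will also be used to evaluate the effect of treatment group on pain scores over time", to mean that a group-by-time comparison is intended. Section II.E names no interaction term, so power for such a test cannot be attributed to the plan.

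**Conclusion.** The point holds as a gap in the primary model and its power statement, not as an arithmetic error. The 90% is unsupported: it is not tied to a stated correlation or to a stated role for the pre-operative ODI. If that score is a sixth outcome in a group and time model, power at 21 per group ranges from about 51% to 76% under compound symmetry, and from about 76% to 95% under autoregressive correlation on the real schedule, over correlations of 0.3 to 0.7. These ranges rest on an inferred 5.2-point post-operative difference, SD 8 at every visit, two-sided testing and complete data; the documents do not give the correlations. The advantage of prespecified baseline adjustment does not depend on knowing the correlation: under both structures examined, with 5.2 points and SD 8, it keeps analytic power above 90% at 21 per group.

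**What to change.** In section II.E, define the dependent variable as ODI at 1, 2, 3, 6 and 12 months. Include treatment group, visit and pre-operative ODI as prespecified terms, whatever the baseline significance test shows.

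In section II.B, restate the power for that model. Give the post-operative difference in points, the post-operative SD, the within-patient correlation and its structure, and whether the test is two-sided. Say whether the 10% refers to post-operative scores.

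The cost is a few sentences. No extra patients, visits or data are needed, since the pre-operative ODI is already collected. The restated power may turn out less favourable than 90% if the difference or SD finally chosen is less favourable than 5.2 and 8.
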